#### 4.5.12 Dietary behaviour

Dietary behaviour (food frequency questionnaire, with the addition of 2 items about nuts and oils). A prudent pattern score is calculated for each participant as follows:

- i) fat spreads and milks are categorised as full fat or reduced fat versions (reduced fat spreads <69g fat/100g, milks <3.5g fat/100g),
- ii) weekly frequencies of consumption are calculated as: never=0, <1/month=0.2, 1-3/month=0.5, 1/ week=1, 2-4/week=3, 5-6/week=5.5, 1/day=7, 2-3/day=17.5, 4-5/day=31.5,  $\geq$ 6/day=42,
- iii) food variables are standardised by subtracting the means and dividing by the SDs for the Hertfordshire Cohort Study (HCS) population,
- iv) the coefficient for each food (Table 2 of [38]) was multiplied by the standardised food variable,
- v) these values are summed resulting in one score for each subject.

The score indicates the participant's compliance with the prudent pattern and is interpreted as a marker of their diet quality (see [41] for further interpretation).

This score will be analysed using linear regression adjusting for baseline prudent pattern score and the same variables as in the primary analysis. The additional questions on consumption of nuts and oils will be summarised descriptively by randomised arm.

## 4.5.13 Brain training behaviours

Brain training behaviours will be summarised descriptively by randomised arm.

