#### Active Lives

The 'Active Lives' module supports users in gradually increasing their levels of physical activity in a manner that is most suited to their present physical capabilities and level of activity. Within this module, there are three sub-modules that users are directed to differentially depending on which is deemed to be most beneficial for them. The 'Getting Active' sub-module provides support and ideas about activities to try to increase individuals' overall levels of physical activity. The 'Breaks from Sitting' sub-module supports individuals in reducing sedentary behaviour by suggesting simple changes that can be made to daily routines. The 'Strength and Balance Training' module provides video demonstrations of simple strength and balance exercises and suggestions about how these can be built into daily activities. The level of exercise difficulty is tailored to the user and their progress. Whilst tailored recommendations will be made about which sub-module users may find most helpful, they will have access to all three sub-modules.

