#### **Secondary Research Objectives:**

Secondary research objectives are to evaluate the effectiveness of the Active Brains digital intervention across a number of other key outcomes at 1 and 5 years:

- 1. Instrumental Activities of Daily Living
- 2. Additional cognitive outcomes (including spatial working memory, attention, and verbal short-term memory)
- 3. Health-related quality of life
- 4. Patient enablement
- 5. Depression
- 6. Changes in the target behaviours (physical activity (including sedentary time), healthy eating, engagement with brain training games)
- 7. Mortality data

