#### 1.4.2 Definition of secondary endpoints

Secondary outcomes will include the following at both 1 year and 5 years: (Further details and derivations are provided in section 4)

- Spatial Working Memory (measured using Self ordered search test)
- Digital Vigilance (attention measured using the 'digit' span task [12])
- Verbal Short-term memory (measured using the paired associates learning [13])
- Modified version of Informant Questionnaire on Cognitive Decline in the Elderly (IQCODE SF) [14]
- Instrumental Activities of Daily living (IADL) [15]
- Quality of Life (EQ5D) [16]
- 12-Item Short Form Health Survey (SF12) [17]
- Patient Enablement Scale [18]
- Brief Geriatric Depression Scale (GDS) [19, 20]
- Short Warwick Edinburgh Mental Well-Being Scale (SWEMWBS) [21]
- Diagnosis of dementia
- Death
- International Physical Activity Questionnaire (IPAQ) plus strength and balance items [22]
- Dietary behaviour (food frequency questionnaire, with the addition of 2 items about nuts and oils) [23]
- Brain training behaviours

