## 2.4 Timing of planned analyses

All primary and secondary analyses will take place when all patients have completed one year follow up. Five-year follow-up is contingent on evidence of effectiveness in changing behaviour and improving cognition at 1 year.

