## 4.5.6 International Physical Activity Questionnaire (IPAQ)

International Physical Activity Questionnaire (IPAQ) plus strength and balance items

MET minutes achieved in each category (walking, moderate activity and vigorous activity) and total MET minutes of physical activity a week are calculated as follows:

- Walking MET-minutes/week = 3.3 \* walking minutes \* walking days
- Moderate MET-minutes/week = 4.0 \* moderate-intensity activity minutes \* moderate days
- Vigorous MET-minutes/week = 8.0 \* vigorous-intensity activity minutes \* vigorousintensity days
- Total physical activity MET-minutes/week = sum of Walking + Moderate + Vigorous MET-minutes/week scores.

Note: Bouts of activity lasting less than 10 minutes duration are not counted. It is also recommended that activity bouts of greater than 3 hours are truncated, i.e., in each category a maximum of 21 hours of activity are permitted a week (3 hours X 7 days).

Total MET minutes will be analysed using linear regression adjusting for baseline MET minutes and the same covariates as in the primary analysis.

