Usage of the Active Brains		Χ	Х	Х		Χ	Х	Х		Х	Х	Х
website throughout												
(including what components												
viewed and any data												
entered online such as at												
goal reviews).												
Objective supporter data								 	1			
Supporters' Usage of Active			Х				Х				Х	
Brains website (throughout												
study)												
Emails sent to participants			Х				Х				Х	
throughout study												
Qualitative data							_					
Interviews with patients					Xa	Xa	Xa	Xa				
about their experiences of												
the study and/or												
intervention												
Interviews with Central							Χ					
Support Facilitators about												
their experiences of the												
study and intervention												
Proxy-Measures (not cohort	group				1				1			
		В	aseline			Years	s 1 and 5			Yea	rs 2-4	
Informant Questionnaire on												
Cognitive Decline in the							Χ					
Elderly (IQCODE) (short												
form) [53]												
Quality of Life (EQ5D5L-												
proxy version 2) to be							Х					
completed by the												
nominated contact person												
(if necessary)												
IADL proxy version to be												
completed by the							Χ					
nominated contact person												
(if necessary)												

\*=notes a measure collected at notes review. ¹ = collected at year one only (not year five also)

<sup>a = process interviews to be conducted 2-12 months after commencement of study; b = baseline only; c = COVID-19 questions only (not long-COVID) at baseline

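### Brain training is only described by arm, sedentary time and the strength and balance items have no planned analysis, and the year-5 depression analysis has no scheduled data

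*SAP*

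**What the plan says.** The sixth secondary objective in SAP 1.3, worded the same way in the Protocol, reads: "Changes in the target behaviours (physical activity (including sedentary time), healthy eating, engagement with brain training games". The SAP sets its secondary objectives "across a number of other key outcomes at 1 and 5 years". SAP 1.4.2 repeats the time points ("Secondary outcomes will include the following at both 1 year and 5 years"), and its list includes the brief Geriatric Depression Scale (GDS), the IPAQ with strength and balance items, diet and brain training.

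The analysis sections treat these differently:

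- **Physical activity (4.5.6).** Walking, moderate and vigorous MET-minutes are summed and the total is regressed with baseline adjustment. A scoring note adds: "Bouts of activity lasting less than 10 minutes duration are not counted". The section heading carries the strength and balance items, but nothing follows for them or for sitting.
- **Diet (4.5.12).** The prudent pattern score is regressed with baseline adjustment.
- **Brain training (4.5.13).** The whole section is: "Brain training behaviours will be summarised descriptively by randomised arm".
- **Depression (4.5.15).** Logistic regression adjusted for baseline depression, under the 4.5 lead-in that places the analyses at 1 and 5 years. The footnote for the GDS in SAP Table 1, as in Protocol Table 2, is: "collected at year one only (not year five also").

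**The concern.** A secondary objective to evaluate effectiveness calls for a between-arm estimate with its uncertainty. For brain training, one of the three main modules, the plan stops at a description. For sedentary time, which the objective names and which has a sub-module that "supports individuals in reducing sedentary behaviour by suggesting simple changes that can be made to daily routines", there is no variable at all. The strength and balance items, which match another sub-module, are collected and then not mentioned again.

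The stake is partly interpretive. SAP 2.4 says: "Five-year follow-up is contingent on evidence of effectiveness in changing behaviour and improving cognition at 1 year". If the form of the brain-training or sitting comparison is settled after year-1 data are seen, it becomes the kind of post hoc decision that SAP 1.1 says the plan is meant to avoid.

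The depression point is separate and simpler: an analysis is planned at a visit where the instrument is not administered.

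**Working it through.** No figure in the documents is in dispute, so the main check sets objective, collection and analysis side by side.

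| Outcome | Where it is promised | Collection (Protocol Table 2, SAP Table 1) | SAP analysis |
|---|---|---|---|
| Physical activity | Objective 6; 1.4.2 | Baseline and follow-up | Regression on total MET-minutes (4.5.6) |
| Sedentary time | Objective 6 | No sitting item shown | None |
| Strength and balance items | 1.4.2, with the IPAQ | Baseline and follow-up | None |
| Diet | Objective 6; 1.4.2 | Baseline and follow-up | Regression (4.5.12) |
| Brain training | Objective 6; 1.4.2 | All three arms at follow-up, no baseline | Descriptive (4.5.13) |
| Depression | Objective 5; 1.4.2 | Baseline and year 1 | Logistic (4.5.15), at 1 and 5 years per 4.5 |

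**Brain training.** The missing baseline rules out within-person change but not a comparison of randomised arms at follow-up. The SAP already does this for Patient Enablement, which has no baseline and is still regressed (4.5.4). It also fits regressions to process measures such as exercise self-efficacy (4.5.16) and locus of causation (4.5.19). The usual-care arm need not be at zero: it receives brief advice on staying mentally active (Protocol, Usual Care), and its use of other websites is not a deviation (SAP 4.2).

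**What an estimate would offer.** Assume full planned recruitment, 70% follow-up at year 1 and a yes/no measure of any use.

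- Respondents per arm: 3,505 × 0.70 = 2,453.5 without cognitive decline; 3,647 × 0.70 = 2,552.9 with it.
- Unadjusted 95% half-width for a difference in proportions, at its widest (50% in each arm): 1.96 × √(2 × 0.5 × 0.5 / n).
- Results: 1.96 × √(0.5 / 2,453.5) = 0.028 and 1.96 × √(0.5 / 2,552.9) = 0.027, or just under 3 percentage points either way.
- For a continuous measure such as sitting time, power at two-sided 0.05 is about Φ(d√(n/2) − 1.96). At d = 0.1 this gives 94% and 95%; at d = 0.05 it falls to 42% and 43%.

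These are illustrations of precision. The plan states no target for these outcomes.

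**The 10-minute rule.** By the SAP formulas, 8 minutes of moderate activity daily would be 4.0 × 8 × 7 = 224 MET-minutes a week but scores 0, whereas 10 minutes scores 4.0 × 10 × 7 = 280. The rule makes the total insensitive to short bouts. It acts only on walking, moderate and vigorous activity, so it cannot delete sitting time, and it is not shown to touch the separate strength and balance items.

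**Depression.** SAP 1.3, 1.4.2 and 4.5 each place it at 1 and 5 years, while both measure tables restrict follow-up collection to year 1. The two cannot both stand. The Protocol objective gives no time point, so the overreach is in the SAP.

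**The case against.** The best defence is that little is truly missing. Total activity, diet and year-1 depression all have models. Brain training is reported by arm, and with samples this large any material difference will be visible; a reader could compute a crude interval from the counts. The games are part of the intervention, no baseline exists, website usage is logged, and brain-training access enters the adherence definition in SAP 4.4.2. The Protocol's general rule (linear, logistic or count regression by outcome type, with 95% CIs) could cover outcomes on which the SAP is silent. The GDS mismatch is blanket wording that the tables correct.

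Much of this stands, and it limits the point. It does not remove it. On brain training the SAP is not silent: it chooses description, in contrast to diet under the same objective. For strength and balance and for sitting, a general rule does not define a variable. The separate process evaluation is given the year 2, 3 and 4 outcomes (SAP 4.6.3), so it is not stated to cover years 1 and 5. The tables do show when the GDS is given, but three places in the SAP still promise a year-5 result.

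A reader might also infer that the 10-minute rule discards exactly the behaviours that the sitting and strength sub-modules promote. The documents do not support that: no bout length is given for either sub-module, and the rule reads as part of the questionnaire's scoring.

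**Conclusion.** The point holds as a gap in the specification of secondary outcomes. One of the three main modules (brain training) has a listed endpoint but no planned effect estimate or interval. Two of the three Active Lives sub-modules (sitting; strength and balance) have no planned between-arm analysis of their target behaviour. The year-5 depression analysis has no scheduled data.

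Two stronger readings are tempting and should be resisted. The first is that these objectives cannot be answered. That fits sedentary time under the present SAP and depression at year 5; it does not fit physical activity, brain training or year-1 depression. The second is that the decision to continue to 5 years would rest on MET-minutes and diet alone. The Protocol makes funding contingent on behaviour and cognition evidence, but neither document says which variables or analyses will inform it.

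The conclusion rests on the two measure tables being the full collection schedule. It leaves open whether the questionnaire version has a sitting item and what format the strength and balance items take, since neither is shown. The primary analysis is untouched.

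**What to change.** 1. **SAP 4.5.13.** Define a brain-training variable (any use, or frequency) and compare each active arm with usual care by logistic or ordinal regression with the primary-analysis covariates and a 95% CI. Omit baseline adjustment, since no baseline is collected.
2. **SAP 4.5.6.** Add between-arm models for the strength and balance items, adjusted for baseline. If the questionnaire has a sitting item, do the same for sitting time; if not, take sedentary time out of the objective.
3. **Depression.** Either remove it from the 5-year objectives, endpoints and analyses in SAP 1.3, 1.4.2 and 4.5, or add the four GDS items to the year-5 form and amend both tables.
4. **Optional.** Report total activity without the 10-minute exclusion as a sensitivity analysis, if shorter bouts were recorded.

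The cost is SAP wording and a few regressions. Brain training and the strength and balance items are already on the collection schedule; sitting time may not be. Adding the GDS at year 5 would put four short items on the form. The downside is a few more secondary comparisons in a plan that makes no multiplicity adjustment, so they should be read as estimates with intervals. The variables should be fixed before year-1 outcome data are examined.

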#### 4.5.14 Problematic Experiences of Therapy Scale (PETS)

Problematic Experiences of Therapy Scale (PETS) The scale comprises 12 items divided into four subscales: "symptoms too severe or aggravated by therapy" (items 1–3), "uncertainty about how to carry out the treatment" (items 4–5), "doubts about treatment efficacy" (items 6–8), and "practical problems" such as lack of time or opportunity, forgetting (items 9–12). All items are scored on a scale ranging from 1 (disagree strongly) to 5 (agree strongly). The scores will be recoded into binary categories as follows: participants who respond "strongly disagree" to all items in a subscale are recoded as "no barriers", and all other scores are recoded as "some barriers or doubts". For each subscale, the categories will be summarised descriptively by intervention arm.

#### 4.5.15 Brief Geriatric Depression Scale (GDS-4)

Brief Geriatric Depression Scale (GDS-4) scores one point for each answer indicating depression (see codebook). Interpretation: 0 = Not Depressed; 1 = Uncertain; 2 to 4 = Depressed. This will be analysed using logistic regression with categories depression vs not depressed/uncertain, adjusting for baseline depression and the same variables as in the primary analysis.

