## Statistical analysis

Intention to treat (ITT) analysis will be performed. If the assumptions for linear modelling are met, linear regression will be used to model the primary outcome and continuous secondary outcomes. If linear modelling assumptions are not met, another appropriate parametric distribution will be sought and a suitable regression model fitted. If no suitable parametric distribution fits the data, a non-parametric approach using quantile regression will be used.

Binary outcomes will be modelled using logistic regression and count outcomes with an appropriate distribution.

All regression models will control for baseline values. The estimates for the overall trial intervention cohorts compared with the control group will be provided with 95% confidence intervals.

Depending on the patterns of missing data, it is likely that we will be using multiple imputation methods for all outcome values that are missing at follow-up, using a chained equations approach to multiple imputation based on baseline data and any available follow up data from other time points. However, we will also include sensitivity analyses - where instead of allowing the model to predict the value of the outcome measure, we set it to a value representing either poor outcome or good outcome. We will also present a sensitivity analysis using complete cases only.

The study will be reported in accordance with the CONSORT (Consolidated Standards of Reporting Trials) statement. The primary analysis will analyse the two trials separately. We

will then explore as a secondary analysis whether both trial datasets can be combined for modelling, particularly for any pre-planned subgroup analyses.

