## 3.5 General principles for reporting and analysis

Analyses will in general be reported using a significance level of 5%, corresponding to 95% confidence intervals unless otherwise stated. There will be no adjustment for multiplicity. Each active intervention arm will be compared to usual care. Descriptive statistics will be reported to 1 decimal place as number and percentage for categorical variables, and mean and standard deviation for continuous variables, or median and interquartile range for variables with a skewed distribution. The groups will be labelled Usual Care, Active Brains and Active Brains plus support.

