## 4.5.7 Quality of Life (EQ5D)

Quality of Life (EQ5D) EQ-5D-5L index values will be derived using the appropriate value set. These utility scores will be analysed using linear regression adjusting for baseline EQ5D score and the same covariates as in the primary analysis.

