## 4.6 Additional analyses

## 4.6.1 Subgroup analyses

For the primary outcome at 1 year, exploratory subgroup analyses will be performed by repeating the primary analysis and including a treatment by covariate interaction term for the following baseline subgroups:

Age: above/below 75 years

Gender: male/female

• Deprivation: IMD more deprived (deciles 1-5) vs less deprived (deciles 6-10)

Comorbidities: < 2 vs ≥ 2

Polypharmacy: number of medications ≥ 5 vs ≤ 4

Health diet: high/low prudent diet score (FFQ)

Physical activity: high/low IPAQ score

Depression: depression vs no depression, based on GDS at baseline

Retirement: retired/working

The same subgroups will be analysed in the same way using the primary outcome at 5 years.

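### SAP 4.5.15 analyses the 0-4 depression score only as depressed versus not; an ordinal analysis of its own three levels would recover a material share of the information

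*SAP*

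**What the plan says.** SAP 4.5.15 describes a four-item scale that "scores one point for each answer indicating depression" and gives its reading as "0 = Not Depressed; 1 = Uncertain; 2 to 4 = Depressed". The analysis is then "logistic regression with categories depression vs not depressed/uncertain, adjusting for baseline depression", together with the primary-analysis covariates. No ordinal, count or full-score analysis is planned.

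Depression is the fifth secondary objective in both documents (Protocol, Secondary Research Objectives; SAP 1.3), and the scale is a listed secondary endpoint (SAP 1.4.2). The footnotes to Protocol Table 2 and SAP Table 1 restrict its post-baseline collection to year one.

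The Protocol's Statistical analysis section names no cut for this scale. Its general rule is: "Binary outcomes will be modelled using logistic regression and count outcomes with an appropriate distribution".

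The SAP does not say whether the baseline term is the category or the score. Elsewhere it names the score, as for quality of life in 4.5.7: "linear regression adjusting for baseline EQ5D score and the same covariates as in the primary analysis". The baseline subgroup in 4.6.1 is binary: "Depression: depression vs no depression, based on GDS at baseline". Taken together, the category is the likelier reading.

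**The concern.** Once scores are cut at 2, a move between 0 and 1, or within 2 to 4, cannot register. If scores of 2 or more are uncommon, the comparison is between two small proportions, and the level that the SAP itself calls uncertain contributes nothing.

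This differs from how the plan treats the other multi-item scales it compares between arms. IQCODE, PEI, IADL, SWEMWBS, SF-12, self-efficacy, mMOS and locus of causation (4.5.3 to 4.5.5, 4.5.8, 4.5.9, 4.5.16, 4.5.17, 4.5.19) all keep their scores. PETS (4.5.14) is also cut, but is only described. No reason for the depression cut is given.

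At stake is the precision of the answer to one secondary objective. A modest shift in mood in either direction is more likely to be reported as inconclusive, and the year-one measurement is the only one after baseline.

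**Working it through.** **The plan's own figures.** Neither document gives a sample size, prevalence or score distribution for depression. The per-arm numbers used below are the Baddeley requirements, which reproduce:
- Standardised effect 0.15, 80% power: 2 × (1.960 + 0.842)² / 0.15² = 698 (stated 698; two subgroups give 1396 per arm in Table 1).
- Standardised effect 0.10, 90% power: 2 × (1.960 + 1.282)² / 0.10² = 2102 (stated 2103).

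**Information kept by the cut.** Let p_i be the category probabilities and P the proportion scoring 2 or more. Under proportional odds, the information in the binary analysis relative to the ordinal one is 3P(1−P) / (1 − Σp_i³).

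Example with an assumed control distribution of 0.68, 0.20, 0.08, 0.03, 0.01 (P = 12%): Σp_i³ = 0.323, so the ratio is 0.3168 / 0.677 = 0.47.

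Over a wider assumed range (beta-binomial scores, inter-item correlation 0.1 to 0.4):

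| Assumed P(score ≥ 2) | Information kept |
|---|---|
| 5% | 0.27–0.50 |
| 10% | 0.38–0.55 |
| 15% | 0.48–0.61 |
| 20% | 0.56–0.65 |
| 30% | 0.70–0.73 |
| 40% | 0.77–0.78 |

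The loss therefore runs from 22% to 73%.

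**Where the loss arises.** Merging only scores 2 to 4 costs little. At 12%, the three levels give 1 − (0.68³ + 0.20³ + 0.12³) = 0.676, against 0.677 for all five. At 40% (0.333, 0.267, 0.200, 0.133, 0.067) the values are 0.880 and 0.933, so three levels keep 94% where the binary cut keeps 77%.

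**Power.** With n per arm and p̄_i averaged over the two arms, V = n(1 − Σp̄_i³)/6 and power = Φ(|ln OR|√V − 1.96).

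Example: n = 1396, OR 0.80, P = 12%.
- Binary: the intervention proportion is 0.0984, p̄ = 0.1092, V = 67.9, power = Φ(0.2231 × 8.24 − 1.96) = 45%.
- Three levels: p̄ = 0.703, 0.188, 0.109, V = 149.9, power = Φ(0.2231 × 12.24 − 1.96) = 78%.

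The 8% and 20% columns use assumed control distributions 0.75, 0.17, 0.05, 0.02, 0.01 and 0.55, 0.25, 0.12, 0.06, 0.02, where the information kept is 0.39 and 0.59. Binary versus ordinal power:

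| n per arm, OR | P = 8% | P = 12% | P = 20% |
|---|---|---|---|
| 1396, 0.80 | 33% vs 71% | 45% vs 78% | 63% vs 86% |
| 1396, 0.85 | 20% vs 45% | 27% vs 52% | 39% vs 60% |
| 2103, 0.80 | 47% vs 87% | 62% vs 92% | 80% vs 96% |

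In these three cases the binary confidence interval on the log-odds scale is 1/√0.59 = 1.3 to 1/√0.39 = 1.6 times as wide.

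**With baseline adjustment.** Two simulations were run under a uniform latent shift.
- 1396 per arm, latent correlation 0.6, shift equivalent to OR 0.80, 150 runs: binary outcome and baseline against a three-level model with baseline score gave 43% vs 83%, 53% vs 85% and 71% vs 84% at 8%, 12% and 20%.
- 2103 per arm, latent correlation 0.7, shift 0.15, 300 runs: against linear analysis of the score, power fell from 74–79% to 41–58% at 5% prevalence, from 83–93% to 59–74% at 10%, and from 91–98% to 78–92% at 20%. Cutting the baseline as well took only 1 to 3 further percentage points of information once the outcome was cut.

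**The case against.** The binary analysis has a fair defence.

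- **The cut is recognised and pre-specified.** It follows the bands in 4.5.15, and one of the references cited for the scale is, by its title, a validity study of short versions for diagnosing a major depressive episode. A case-level comparison is a legitimate question, and a plan need not justify every secondary cut. This stands, and is why the point is about efficiency only.
- **The gain depends on proportional odds.** Every figure above assumes a common odds ratio or a uniform latent shift. An effect concentrated at the case threshold would shrink or reverse the advantage, and no such scenario was tested. When high scores are rare, the common odds ratio is also driven mainly by the split at 0 versus 1 or more: at 12% that split alone carries 3 × 0.68 × 0.32 / 0.677 = 0.96 of the information. This stands, and is the reason to keep the case comparison and to report odds ratios at each cut.
- **Planned enrolment exceeds the numbers used.** In the decline trial, 3647 × 0.70 = 2553 per arm at one year. At OR 0.80 power is then 87% vs 98% at 20% prevalence, a gain of 11 points, but still 54% vs 92% at 8%. Completion of this scale may also fall short of 70%, because the telephone chase described under Measures in the Protocol covers only reasoning, IADL and EQ-5D.
- **The contrast with other scales is weak.** Most of those are longer than four one-point items. This partly stands.

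A reader might infer that the cut always discards at least half of the information. The documents do not support that: no distribution is given, the loss is about 41% in the 20% case, and at 30% to 40% between 70% and 78% is kept. A reader might also infer that the SAP explicitly cuts the baseline, or that depression is a safety endpoint. It says neither.

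**Conclusion.** The point holds as a cheap improvement, not as an error or a contradiction with the Protocol. The planned binary model is the only between-arm analysis of a named secondary objective. Under roughly proportional odds it loses about a quarter to over a half of the information (22% to 73% over assumed prevalences of 5% to 40%). The loss is half or more in every scenario only at about 5%, in some at 10% to 15%, and in none at 20% or above.

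The power gain is not uniformly large. It reaches about 40 points when scores of 2 or more are rare. At 20% prevalence it is 13 points in the adjusted simulation at 1396 per arm (71% vs 84%, Monte Carlo error 3 to 4 points each) and 11 points at planned enrolment.

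Prevalences, score distributions, correlations and effect sizes are all assumptions. The direction of the result, and the finding that the three stated levels recover most of the loss, hold across the range tried. Depression is one of seven additional secondary objectives and is not powered for, so the stakes are modest.

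**What to change.** In SAP 4.5.15:

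1. Make the main between-arm analysis a proportional-odds logistic regression of the one-year GDS-4 on the three levels 0 / 1 / 2-4, or on the 0-4 score. Name one of the two in advance.
2. Adjust for the baseline GDS-4 score and the primary-analysis covariates, and say explicitly that the baseline term is the score.
3. Keep depressed (2-4) versus not as a pre-specified supportive result, with proportions by arm.
4. Report cut-point-specific odds ratios as the check on proportional odds.
5. State that the analysis is at year one only. SAP 4.5 opens by placing secondary outcomes at years 1 and 5, but this scale is not collected at year 5.

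The cost is SAP wording. The data are already collected and the model is a standard ordinal command in Stata. The downside is that the main estimate becomes a common odds ratio, which relies on approximate proportional odds and is less directly a comparison of cases. The change should be made before unblinding, since choosing the ordinal model afterwards would be the kind of post hoc decision that SAP 1.1 aims to avoid.
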